11.1. Overview

This section defines the types of safety data that will be collected under this protocol and outlines the procedures for appropriately collecting, grading, recording, and reporting those data. Adverse events that are classified as serious according to the definition of health authorities must be reported promptly to the Supporter. Appropriate notifications per local institutional guidelines will also be made to Institutional Review Boards (IRBs) and health authorities.

Information in this section complies with ICH Guideline E2A: Clinical Safety Data Management: Definitions and Standards for Expedited Reporting, ICH Guideline E-6: Guideline for Good Clinical Practice, 21CFR Parts 312 and 320, and applies the standards set forth in the National Cancer Institute (NCI), Common Terminology Criteria for Adverse Events (CTCAE), Version 4.0:

https://www.acrin.org/Portals/0/Administration/Regulatory/CTCAE 4.02 2009-09-15 QuickReference 5x7.pdf

11.2. Definitions

11.2.1. Adverse Event (AE)

Any untoward or unfavorable medical occurrence associated with the subject's participation in the research, whether or not considered related to the subject's participation in the research (modified from the definition of adverse events in the 1996 International Conference on Harmonization E-6 Guidelines for Good Clinical Practice) (from OHRP "Guidance on Reviewing and Reporting Unanticipated Problems Involving Risks to Subjects or Others and Adverse Events (1/15/07)":

https://www.hhs.gov/ohrp/sites/default/files/ohrp/policy/advevntguid.pdf

11.2.1.1. Suspected Adverse Event

Any adverse event for which there is a reasonable possibility that the investigational drug caused the adverse event. For the purposes of safety reporting, 'reasonable possibility' means there is evidence to suggest a causal relationship between the drug and the adverse event. A suspected adverse reaction implies a lesser

degree of certainty about causality than adverse reaction, which means any adverse event caused by a drug (21 CFR 312.32(a)).

11.2.1.2. Unexpected Adverse Event

An adverse event or suspected adverse reaction is considered "unexpected" if it is not listed in the package insert or is not listed at the specificity, severity or rate of occurrence that has been observed. "Unexpected" also refers to adverse events or suspected adverse reactions that are mentioned in the Investigator Brochure or package insert as occurring with a class of drugs or as anticipated from the pharmacological properties of the drug, but are not specifically mentioned as occurring with the particular drug under investigation (21 CFR 312.32(a).

11.2.2. Serious Adverse Event (SAE)

An adverse event or suspected adverse reaction is considered "serious" if, in the view of either the Investigator or Supporter, it results in any of the following outcomes (21 CFR 312.32(a)):

- Death.
- A life-threatening event: An AE or SAE is considered "life-threatening" if, in the view of either the investigator or Supporter, its occurrence places the subject at immediate risk of death. It does not include an AE or SAE that, had it occurred in a more severe form, might have caused death.
- Inpatient hospitalization or prolongation of existing hospitalization.
- Persistent or significant incapacity or substantial disruption of the ability to conduct normal life functions.
- Congenital anomaly or birth defect.
- Important medical events that may not result in death, be life threatening, or require hospitalization may be considered serious when, based upon appropriate medical judgment, they may jeopardize the subject and may require medical or surgical intervention to prevent one of the outcomes listed above.
- Elective hospitalizations or hospital admissions for the purpose of conduct of protocol mandated procedures are not to be reported as an SAE unless hospitalization is prolonged due to complications.

11.3. Grading and Attribution of Adverse Events

11.3.1. Grading Criteria

The study site will grade the severity of adverse events experienced by the study subjects according to the criteria set forth in the National Cancer Institute's Common Terminology Criteria for Adverse Events (CTCAE) *version 4.0.* This document (referred to herein as the NCI-CTCAE manual) provides a common language to describe levels of severity, to analyze and interpret data, and to articulate the clinical significance of all adverse events. The NCI-CTCAE has been reviewed by the Principal Investigator and has been deemed appropriate for the subject population to be studied in this protocol.

Infections will be graded using the study-specific scale as described below:

Grade 1 = asymptomatic; clinical or diagnostic observation only; intervention with oral antibiotic, antifungal, or antiviral agent only; no invasive intervention required

Grade 2 = symptomatic; intervention with intravenous antibiotic, antifungal, or antiviral agent; invasive intervention may be required

Grade 3 = any infection associated with hemodynamic compromise requiring pressors; any infection necessitating ICU level of care; any infection necessitating operative intervention; any infection involving the central nervous system; any infection with a positive fungal blood culture; any proven or probable aspergillus infection; any tissue invasive fungal infection; any pneumocystis jiroveci infection

Grade 4 = life-threatening infection

Grade 5 = death resulting from infection

All other adverse events will be graded on a scale from 1 to 5 according to the following standards in the NCI-CTCAE manual:

Grade 1 = mild adverse event.

Grade 2 = moderate adverse event.

Grade 3 = severe and undesirable adverse event.

Grade 4 = life-threatening or disabling adverse event.

Grade 5 = death.

Infection events grade 2 or higher; and all other events CTCAE grade 2 or higher will be recorded on the appropriate AE form for this study.

For grading an abnormal value or result of a clinical or laboratory evaluation (including, but not limited to, a radiograph, an ultrasound, an electrocardiogram etc.), a treatmentemergent adverse event is defined as an increase in grade from baseline or from the last post-baseline value that does not meet grading criteria. Changes in grade from screening to baseline will also be recorded as adverse events, but are not treatmentemergent. If a specific event or result from a given clinical or laboratory evaluation is not included in the NCI-CTCAE manual, then an abnormal result would be considered an adverse event if changes in therapy or monitoring are implemented as a result of the event/result.

11.3.2. Attribution Definitions

The relationship, or attribution, of an adverse event to the study therapy regimen will initially be determined by the site investigator and recorded on the

appropriate AE/SAE form. Final determination of attribution for safety reporting will be determined by the Supporter after consultation with the Investigator. The relationship of an adverse event to study therapy regimen will be determined using the descriptors and definitions provided in Table 2 below.

For additional information and a printable version of the NCI-CTCAE manual, consult the NCI-CTCAE web site:

https://www.acrin.org/Portals/0/Administration/Regulatory/CTCAE 4.02 2009-09-15 QuickReference 5x7.pdf

Table 2. Attribution of Adverse Events							
Code	Descriptor	Relationship (to primary investigational product and/or other concurrent mandated study therapy or study procedure)					
Unrelated Category							
1 Related Categories	Unrelated	The adverse event is clearly not related: there is insufficient evidence to suggest a causal relationship.					
nemieu culegones		The adverse event has a					
2	Possible	reasonable possibility to be related; there is evidence to suggest a causal relationship.					
3	Definite	The adverse event is clearly related.					

Table 2. Attribution of Adverse Events

Attribution of adverse event to tacrolimus, MMF/MPA, and prednisone will not be assessed in this study because these medications are used as standard of care for kidney transplant recipients.

Attribution assessment for the following study interventions will be made when a SAE is reported:

Study Therapy:

Envarsus

11.4. Collection and Recording of Adverse Events 11.4.1. Collection Period

Adverse events will be collected from the time of first study mandated activity

until a subject completes study participation or until 30 days after he/she prematurely withdraws (without withdrawing consent), or is withdrawn from the study.

11.4.2. Collecting Adverse Events

Adverse events (including SAEs) may be discovered through any of these methods:

- Observing the subject.
- Interviewing the subject [e.g., using a checklist, structured questioning, diary, etc.] .
- Receiving an unsolicited complaint from the subject.
- In addition, an abnormal value or result from a clinical or laboratory evaluation can also indicate an adverse event, as defined in Section 14.3, *Grading and Attribution of Adverse Events.*

11.4.3. Recording Adverse Events

Throughout the study, the investigator will record adverse events and serious adverse events as described previously (Section 14.2, *Definitions*) on the appropriate AE/SAE form regardless of the relationship to study therapy regimen or study procedure.

Once recorded, an AE/SAE will be followed until it resolves with or without sequelae, or until the end of study participation, or until 30 days after the subject prematurely withdraws (without withdrawing consent)/or is withdrawn from the study, whichever occurs first.

11.5. Reporting of Serious Adverse Events and Adverse Events

11.5.1. Reporting of Serious Adverse Events to Sponsor

This section describes the responsibilities of the site investigator to report serious adverse events to the Supporter via the AE/SAE form. Timely reporting of adverse events is required by 21 CFR and ICH E6 guidelines.

The PI will report all serious adverse events (see Section 13.2.3, *Serious Adverse Event*), to the Supporter, regardless of relationship or expectedness, within 24 hours of discovering the event.

For serious adverse events, all requested information on the AE/SAE CRF will be provided. However, unavailable details of the event will not delay submission of the known information. As additional details become available, the AE/SAE form will be updated and submitted to the Supporter.

11.5.2. Reporting of Adverse Events to IRB

The investigator shall report adverse events, including expedited reports, in a timely fashion to their respective IRB in accordance with their local IRB guidelines.

11.6. Pregnancy Reporting

The investigator shall be informed immediately of any pregnancy in a study participant or a partner of a study participant. A pregnant participant shall not receive MMF. The investigator shall counsel the participant and discuss the risks of continuing with the pregnancy and the possible effects on the fetus. Monitoring of the pregnant participant shall continue until the conclusion of the pregnancy.

The investigator shall report to the Supporter all pregnancies within 1 business day of becoming aware of the event. All pregnancies identified during the study shall be followed to conclusion and the outcome of each must be reported. When possible, similar information shall be obtained for a pregnancy occurring in a partner of a study participant.

Information requested about the delivery shall include:

- Gestational age at delivery
- Birth weight, length, and head circumference
- Gender
- Appearance, pulse, grimace, activity, and respiration (APGAR) score at 1 minute, 5 minutes, and 24 hours after birth, if available
- Any abnormalities.

For all pregnancy complications that result in a congenital abnormality, birth defect, miscarriage, and medically indicated abortion, an SAE shall be submitted to the Supporter using the SAE reporting procedures described above.

11.7. Reporting of Other Safety Information

An investigator shall notify the site IRB according to the site's IRB guidelines when an "unanticipated problem involving risks to participants or others" is identified, which is not otherwise reportable as an adverse event.

12. Statistical Considerations and Analytical Plan

This is a single center prospective study comparing incidence of BK infection in rapid metabolizers converted from tacrolimus to Envarsus against a recent historical control of rapidly metabolizing recipients who had BK screening at similar points, but remained on tacrolimus.

This study has both safety and efficacy endpoints.

We will use standard descriptive statistics for continuous and categorical data to define adverse events, and clinical outcomes as noted above. Analysis will be undertaken utilizing UAB statistical support in the School of Public Health and Transplant Quality, Informatics and Outcomes.

The enrollment plan is based on a power calculation. A population of 100 patients is calculated

to show significant difference for p value < 0.05.

Our results will be submitted to national/international nephrology/transplant meetings, and as a primary manuscript reporting the primary efficacy and safety data, and secondary manuscripts reporting different secondary endpoints, as appropriate.

We expect the changes over time in these assays to be approximately linear. If after examination of the data, this appears to not be the case, then we will either transform the assay measures or model the time axis time points as an unordered factor (similar to repeated measures ANOVA, but without the requirement for fully balanced data).

We will use descriptive analyses to summarize subject characteristics of our study population. Dichotomous variables will be summarized as proportions with 95% confidence intervals. Continuous variables will be summarized using means, standard deviations, and 95% confidence intervals if they are symmetric and unimodal. Otherwise, they will be summarized using the median and the interquartile range. Simple t-, chi-squared, or Fisher's exact test, as appropriate, will be used to compare quantitative measures across treatment groups. The following variables will be summarized:

- Baseline and demographic characteristics
- Use of concomitant medications
- Reasons for early termination
- All reportable AEs

No formal interim analyses of this study are planned.

13. Identification and Access to Source Data

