2.3.2. Clinical Studies of Rapid Metabolizers and BK Infection

Tholking et al have demonstrated and increased association with BK infection among transplant patients with low C/D ratios compared to those with high C/D ratios.

In a single center retrospective study¹ of 248 patients designed to investigate effect of metabolism on renal function, patients were grouped according to their C/D ratio (< 1 for fast metabolizers, and >1.55 for slow metabolizers) and had eGFR assessed at 2, 3, 6, 12, and 24 months. Incidence of BK viremia was 8% in the fast group and 1% in the slow group. BKVN was only diagnosed in the fast group with a 4% incidence.

The fast metabolizer group also had significantly higher rates of CNI nephrotoxicity. The authors hypothesized that these findings are related to overexposure of tacrolimus during the peak hours after tacrolimus intake.

A second retrospective study⁴ assessed C/D ratio in 192 renal transplant patients, 92 of whom had BK viremia and 92 whom did not. Patients with BK viremia had lower tacrolimus C/D ratios at 1, 3, and 6 months post transplant.

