3.1. Description of Study Design

This will be a single center prospective case control study. We expect 40% of patients will develop BK viruria, 20% BK viremia, 5% BK viral nephropathy (BKVN). Patients will be managed using standard of care for our center (thymoglobulin induction, tacrolimus/mycophenolate/prednisone). Target tacrolimus level is 8-12 ng/mL for the first 6 months post transplant and 6-9 ng/mL thereafter. BK urine/serum is routinely monitored during the first year post transplant. A population of 100 patients is calculated to show significant difference for p value < 0.05.

Population:

Study Group: Post transplant patients (kidney transplant alone) with standard of care immunosuppression, no prior rejection, prior BK or opportunistic infection, and negative BK screening at post-transplant month 1, who have a tacrolimus concentration/dose of < 1 and a steady state therapeutic level will be eligible. Patients who consent to participate will be converted to Envarsus at 20% reduction in tacrolimus dose.

Control Group: Post transplant patients (kidney transplant alone performed between 10-2016 and time of consideration for study control group) with standard of care immunosuppression, no prior rejection, prior BK or opportunistic infection, who had a negative BK screening at post-transplant month 1 and tacrolimus concentration/dose of < 1 at post-transplant month 1, and BK data available for months 2, 3, 6, 9, 12 post transplant.

Study visits: Post-transplant Months 2, 3, 6, 9, 12

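### The comparison with historical controls plans no adjustment for baseline differences, so measured case-mix differences pass straight into the BK estimate.

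*Combined protocol and SAP*

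**What the plan says.** Section 3.1 (Description of Study Design) forms two non-randomised groups. On one side, "Patients who consent to participate will be converted to Envarsus". On the other are kidney-alone recipients transplanted from October 2016 onwards who stayed on tacrolimus. Section 12 describes the comparison as one "against a recent historical control of rapidly metabolizing recipients".

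For analysis, Section 12 offers this: "Dichotomous variables will be summarized as proportions with 95% confidence intervals". It then adds: "Simple t-, chi-squared, or Fisher's exact test, as appropriate, will be used to compare quantitative measures across treatment groups". The list of variables that follows begins with "Baseline and demographic characteristics" and continues with concomitant medications, early termination and adverse events. BK infection is not on it. The one modelling statement in Section 12 concerns the shape of assay changes over time and names no covariates.

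Comparability therefore rests on eligibility alone. Both groups in Section 3.1 are patients "with standard of care immunosuppression, no prior rejection, prior BK or opportunistic infection", with a negative BK screen at month 1 and a C/D ratio below 1.

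**The concern.** Restriction narrows the case mix without equalising it. The protocol's own background points to factors that remain free to differ:

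- **C/D ratio.** Section 2.3.2 reports: "Patients with BK viremia had lower tacrolimus C/D ratios at 1, 3, and 6 months post transplant". Eligibility caps C/D at 1 and lets it vary below that.
- **Donor and recipient characteristics.** Section 2.1.2 cites them as BK risk factors. Section 4.1.1 admits both deceased-donor and living-donor recipients, and adults of any age.
- **Degree of immunosuppression.** Section 2.1.1 calls this the most consistent risk factor. Sections 4.1.1 and 6.1.2 set a minimum mycophenolate dose, not a fixed one.

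The planned baseline summary would reveal an imbalance, but no rule says what follows from it. Two things are at stake. An unadjusted difference credits or debits Envarsus with whatever the case mix contributes. And if adjustment is considered only once the data are in hand, the choice can be made after the results are known.

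**Working it through.** **The plan's own figure.** The plan gives no figure for confounding. Its one calculation, 100 patients at p < 0.05, cannot be reproduced uniquely because effect size, power, sidedness and allocation are not stated. For example, 40% against 15%, two-sided with 80% power, gives 98 in total. Halving 40% to 20% would need 164. No allowance for confounding is visible.

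**Inputs, all assumptions for illustration.**
- Control event rate 40%. Section 3.1 says "We expect 40% of patients will develop BK viruria"; this stands in for the composite.
- 50 per group. The plan says only 100 patients.
- One binary risk factor, present in 50% of controls and in a share *q* of converts, with risk ratio RR = 1.5, 2 or 3. At these rates the corresponding odds ratios are about 2.0, 3.1 and 6.0.
- No drug effect at first.

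**Formulas.** The rate without the factor is p0 = 0.40 / (0.5·RR + 0.5), which gives 0.320, 0.267 and 0.200. The convert rate is p0·(q·RR + 1 − q). The spurious difference is 0.40 minus that. For RR = 2 and q = 0.3: 0.267 × 1.3 = 0.347, so 5.3 points.

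**Unadjusted tests, exact two-sided rejection at 0.05.** With no imbalance the rates are 5.2% (chi-squared) and 3.2% (Fisher).

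| Converts exposed | RR | Convert rate | Spurious difference (points) | Chi-squared | Fisher |
|---|---|---|---|---|---|
| 30% | 1.5 | 0.368 | 3.2 | 6.4% | 4.1% |
| 30% | 2 | 0.347 | 5.3 | 8.6% | 5.7% |
| 30% | 3 | 0.320 | 8.0 | 13.2% | 9.3% |
| 40% | 1.5 | 0.384 | 1.6 | 5.5% | 3.4% |
| 40% | 2 | 0.373 | 2.7 | 6.0% | 3.8% |
| 40% | 3 | 0.360 | 4.0 | 7.1% | 4.6% |

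**Adjusted analysis, same scenarios.** This is logistic regression on treatment and four covariates (the risk factor plus three unrelated to outcome, one of them shifted by 0.3 SD), standardised to the pooled sample, with delta-method standard errors and 20,000 simulations per scenario. Bias was at most 0.12 points. False positives were 5.9% to 6.5% uncorrected. With the variance multiplied by 100/94 and a t reference on 94 degrees of freedom they were 4.9% to 5.5%. Smaller repeat simulations gave 4.8% to 5.9%.

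**Reverse direction.** Let Envarsus truly halve the risk and let 70% of converts carry the factor. The convert rate becomes 0.5·p0·(0.7·RR + 0.3) = 0.216, 0.227 and 0.240. Chi-squared power falls from 60% (balanced, 0.20 against 0.40) to 52%, 46% and 40%. The corrected adjusted analysis has 58%, 63% and 67%. Part of that gain is arithmetic: at the pooled 60% exposure the true difference is 21.3 points (RR 2) or 22 points (RR 3), not 20.

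**When adjustment costs power.** With balanced groups, adjusted power was roughly 55% to 59% across simulations, against 60% unadjusted. With 30% of converts exposed at RR 2 it was about 51%, against an unadjusted 72% that is inflated by bias.

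**The case against.** - **The quoted sentence is descriptive.** It sits among summaries of subject characteristics, refers to quantitative measures, and is not tied to the BK composite. That is correct: the plan assigns no explicit analysis to its primary endpoint. The simple tests are the natural reading because no other between-group method is named. If they are not meant for the composite, the need to name an analysis is greater.
- **Restriction already deals with confounding.** It does in part. The point concerns only what remains.
- **The gain is small in places.** This stands. Fisher's test stays below 5% in four of the six null scenarios, and in those the corrected adjusted method rejects slightly more often. The larger risk ratios are strong effects that nothing in the documents establishes. The main gain is removal of bias.
- **The covariate list is a judgement.** This also stands. Section 2.1.2 does not single out donor type or age, Section 2.1.1 does not name mycophenolate, and Section 2.3.2 shows no gradient within C/D below 1. If the real confounder is left off the list nothing is gained: at RR 2 and 30% exposed, bias stayed near 5.4 points, false positives near 9%, and intervals were about 5% wider.
- **Adjustment cannot repair era or selection effects.** Agreed. Controls must have BK data at every visit to month 12, while converts may leave early. The serum BK exclusion at entry (Section 4.1.2) has no stated counterpart for controls.

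**Conclusion.** The concern holds. The plan compares non-randomised groups, names only unadjusted tests and has no rule for baseline imbalance. Measured differences therefore enter the BK estimate in whichever direction they run. In the null scenarios the distortion is 1.6 to 8.0 points, with chi-squared false positives of 5.5% to 13.2%; it is minor at the low end. These sizes rest wholly on the assumed control rate, group sizes, risk ratios and imbalances. The omission itself does not depend on them. This is an inexpensive improvement to the plan; the trial's actual bias is unknown.

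**What to change.** Name as the primary analysis a covariate-adjusted difference in BK infection by month 12 with a 95% confidence interval, for example logistic regression standardised to the pooled sample with the small-sample correction above.

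- Fix the covariates before outcomes are compared, and keep the list short: at a 40% rate, 100 patients yield about 40 events. Candidates are month-1 C/D ratio, donor type, recipient age and baseline mycophenolate dose.
- Define each at the same time point in both groups, post-transplant month 1, and abstract it the same way. Appendix 1 collects medication data only from Visit 1, so converts' month-1 doses must also come from charts.
- Use no post-entry values, because Section 6.1.2 allows mycophenolate changes for infection.
- Keep the unadjusted test as a sensitivity analysis.
- State calendar era and unmeasured factors as limits. State entry rules written for one group only as limits too, or reconcile those passages.

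The cost is SAP wording, a common index date and about four chart items per patient. At 50 per group, corrected intervals were between 3% narrower and 6% wider than unadjusted ones. Without the correction they were 7% narrower to 2% wider, but false positives rose to about 6%. If the groups turn out balanced, expect a small loss of power.
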